STATISTICS Primary Analysis Plan	
Sample size calculation: We calculated that a sample size of 40 wounds (20 matrix-treated vs 20 untreated) would give us 90% power to detect a difference of 8.5 vs 6 weeks (SD=3) of wound closure duration between matrix treated vs untreated wounds with a two-sided alpha of 0.05.
 
Recruitment plan: We will recruit our cohort of 6-10 patients from various settings including the Stanford EB clinic (~100 RDEB patients), our clinical research database (75 RDEB patients), and the Epidermolysis Bullosa Clinical Research Consortium (EBCRC) (290 RDEB patients). Many of these patients have already received a clinical and/or genetic diagnosis of RDEB and have detailed medical and wound histories recorded

Rationale for Number of Subjects	This sample size calculation is based on our prior natural history study of 720 RDEB wounds for 6 months in 13 RDEB adult and pediatric participants. We anticipate that the majority of pediatric wounds will be the recurrent type. If the Spincare matrix decreases the duration of wound closure, then this clinical trial would show a novel wound healing device that may improve wound closure duration in difficult to heal RDEB wounds. We would assess the secondary endpoints to determine if a 2.5 week longer wound closure is clinically meaningful and associated with wound specific decreases in pain and itch.

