2.5.9 Schedule of study visits

	Randomized Phase												Open-Label Phase				
	Day 0	Day 1	Week 1	Week 2	Month 1	Week 6	Month 2	Week 10	Month 3	Week 14	Month 4 ^a	Baseline ^b	Month 1	Month 2	Month 3	Month 4	
	Clinic Visit		Phone Call										Phone Call				
Medical History	X	X	X	X	X		X		X		X	X	X	X	X	X	
Adverse Events		X	X	X	X		X		X		X	X	X	X	X	X	
Vital Signs	X	X															
Direct Skin examination	X	X															
IGA grading			X		X		X		X		X	X	X	X	X	X	
Wound selection and randomization	X												X ^c				
Application of matrix in clinic	X	X															
Application of matrix at home			X	X	X	X	X	X	X			X	X	X	X	X	
Wound culture	X						X				X						
Itch and pain scores	X		X	X	X	X	X	X	X	X	X	X	X	X	X	X	
Caregiver survey									X		X						
Wound size measurements	X	X	X		X		X		X		X	X	X	X	X	X	
Photographs by investigator	X	X															
Photographs at home			X		X	X	X	X	X	X	X	X	X	X	X	X	

Study timeline:

Randomized Phase:

Day 0: in person visit; randomization of wounds with wound photography, application of matrix and monitoring of adverse events (matrix application within 30 days of screening).

Day 1: in person assessment of wounds.

Day 2 (optional): review of wounds with photographs.

Telehealth assessment at **Week 1, Week 2, Month 1, Month 2, Month 3 and Month 4** (a window of ± 7 days for the monthly scheduled visits is expected).

Participant will provide pain and itch surveys and photographs every two weeks.

Additional visits (over secure video platform or phone calls), and reapplication of matrix by caregiver may be scheduled if deemed necessary.

Open-Label Phase:

Baseline Open-Label: telehealth assessment; selection of wounds and baseline wound photography, application of matrix and monitoring of adverse events.

Telehealth assessment at **Open-Label Month 1, Open-Label Month 2, Open Label Month 3 and Open-Label Month 4** (a window of ± 7 days for the monthly scheduled visits is expected). Participant will provide pain and itch surveys and photographs at every Open-Label Month visit. Participants can reapply up to once a week. Additional visits (over secure video platform or phone calls), and reapplication of matrix by caregiver may be scheduled if deemed necessary.

a The **Baseline Open-Label** visit could be done during the **Randomized Phase Month 4**.

b The **Baseline Open-Label** visit could be done up to two weeks after the **Randomized Phase Month 4** visit.

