2.6 Study outcome evaluations

2.6.1 Study endpoints

Primary endpoint:

Comparison of the duration of wound closure (weeks) of matrix treated wounds vs control wounds from baseline to Month 4. Wound photos will be captured bi-weekly by caregivers.

Secondary endpoints:

1. Comparison of application site adverse events (burning, erythema, pain) between matrix treated wounds vs control wounds after application;
2. Comparison of wound pain (Wong-Baker FACES scale) between matrix treated wounds vs control wounds at month 1, month 2, month 3, month 4 (prior to matrix application);
3. Comparison of wound itch (Itch NRS/Itchy Man scale) between matrix treated wounds vs control wounds at month 1, month 2, month 3, month 4 (prior to matrix application);
4. Comparison of wounds that reach >50% healing from baseline in matrix vs control wounds at month 1, 2, 3, 4;
5. Comparison of wounds that reach >70% healing from baseline in matrix vs control wounds at month 1, 2, 3, 4.

Exploratory endpoints:

1. Comparison of caregiver responses on wound dressing ease of use on matrix treated wounds vs control wounds with the Caregiver Global Impression of Change (CrGI);
2. Comparison of change in wound cultures between matrix treated wounds vs control wounds at Month 2 and Month 4,

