2.6.2 Sample size determination

We calculated that a sample size of 40 wounds (20 matrix-treated vs 20 untreated) would give us 90% power to detect a difference of 8.5 vs 6 weeks (SD=3) of wound closure duration between untreated vs matrix treated wounds respectively a two-sided alpha of 0.05. This sample size calculation is based on our prior natural history study of 720 RDEB wounds for 6 months in 13 RDEB adult and pediatric participants. We anticipate that the majority of pediatric wounds will be the recurrent type. If the Spincare matrix reduces the duration of wound closure, then this clinical trial would show a novel wound healing device that may improve wound closure duration in difficult to heal RDEB wounds. We would assess the secondary endpoints to determine if a 2.5-week shorter wound closure is clinically meaningful and associated with wound specific decreases in pain and itch.

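### Wound area is scheduled at baseline and every month, but the secondary healing endpoints use it only as eight threshold counts, which discards information in about 20 pairs

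*Combined protocol and SAP*

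**What the plan says.** The table in section 2.5.9 has a row for "Wound size measurements", marked at Day 0, Day 1, Week 1 and Months 1, 2, 3 and 4. Size is an area: section 2.4.3 sets eligibility at 10 cm² per wound.

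Section 2.6.1 uses that area in two secondary endpoints. Endpoint 4 is "Comparison of wounds that reach >50% healing from baseline in matrix vs control wounds at month 1, 2, 3, 4". Endpoint 5 is "Comparison of wounds that reach >70% healing from baseline in matrix vs control wounds" at the same four months. No test, lead time point or multiplicity rule is given for them, and no endpoint uses area or percent area change as a quantity. The primary endpoint is on a continuous scale, in weeks.

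Section 2.5.7 treats closure as more than 90% healing, assessed every two weeks for 16 weeks. The planning assumption in section 2.6.2 is "difference of 8.5 vs 6 weeks (SD=3) of wound closure duration between untreated vs matrix treated wounds", for which it claims 90% power with 20 wounds per arm. The synopsis gives the same figures with the arms in the other order: "detect a difference of 8.5 vs 6 weeks (SD=3) of wound closure duration between matrix treated vs untreated wounds". It then speaks of a longer closure as the possible benefit. No power is stated for endpoints 4 and 5.

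**The concern.** A threshold count keeps only which side of the line a wound is on. In a matched design it then uses only the pairs whose two wounds fall on different sides. With 20 pairs few may be left, although the measurements that would show the size of the difference are already scheduled.

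The plan gives these endpoints work to do. Section 2.6.2 relies on the secondary endpoints to judge whether the primary difference is clinically meaningful, and section 2.6.3 looks to the study for data to design larger trials. Both uses are served better by an effect estimate and a variance for area than by eight overlapping counts.

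**Working it through.** **Inputs.** From section 2.6.2: 20 wounds per arm, 8.5 (untreated) and 6 weeks (matrix), SD 3, two-sided alpha 0.05. From section 2.5.7: closure is more than 90% healed, and 16 weeks is 4 months, so Months 1 to 4 are taken as Weeks 4, 8, 12 and 16. Not in the documents and therefore assumed: the healing path, the shape of the distribution, the within-pair correlation, the reading error, the test, and no re-opening.

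**1. The plan's own figure.** For two independent groups, SE = 3 × √(2/20) = 0.949, 2.5/0.949 = 2.635, and power = Φ(2.635 − 1.96) = 75%, not 90%. A paired analysis has SD of differences 3√(2(1 − ρ)) and reaches 90% at about ρ = 0.34 (normal approximation) or 0.40 (t-test). The stated figure concerns the primary endpoint and is not the point here. It does suggest trying correlations of 0, 0.34 and 0.5.

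**2. Ceiling, section 2.6.2 reading.** The share already more than 90% closed at week w is Φ((w − mean)/3).

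| Week | Matrix (mean 6) | Control (mean 8.5) |
|---|---|---|
| 4 | 25% | 7% |
| 8 | 75% | 43% |
| 12 | 97.7% | 87.8% |
| 16 | 99.96% | 99.4% |

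A wound past 90% is past 50% and 70%, so these are lower bounds for the Month 3 and Month 4 counts. Exact McNemar needs at least six discordant pairs, all in one direction (2 × 0.5⁶ = 0.03, but 2 × 0.5⁵ = 0.06). Even at the 90% line, independent wounds at Week 12 give 20 × (0.977 × 0.122 + 0.023 × 0.878) = 2.8 discordant pairs on average.

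**3. Other visits, linear path.** Let percent healed be 90w/T, capped at 100, with T the closure time. A wound then exceeds h% when T < 90w/h. For 50% at Week 8 the limit is 14.4 weeks, which gives Φ(2.80) = 99.7% for matrix and Φ(1.97) = 97.5% for control. That is a fifth count at ceiling. Three remain: >50% at Month 1 and >70% at Months 1 and 2.

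**4. Power, same model.** 20,000 simulated trials of 20 pairs, normal times, no reading error, correlation 0 / 0.34 / 0.5:

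| Analysis | Power, % |
|---|---|
| Paired t on percent area, Month 1 | 66 / 82 / 90 |
| Paired t, Month 2 | 61 / 74 / 82 |
| Paired t, Month 3 | about 20 |
| Paired t, Month 4 | 0 |
| Paired t, mean of four months | 70 / 85 / 93 |
| McNemar >50%, Month 1: exact | 40 / 47 / 51 |
| same, uncorrected | 50 / 59 / 65 |
| McNemar >70%, Month 1: exact | 30 / 34 / 36 |
| same, uncorrected | 42 / 50 / 56 |
| McNemar >70%, Month 2: exact | 20 / 20 / 20 |
| same, uncorrected | 36 / 42 / 46 |
| Other five counts, exact | 0 |

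Relative loss at the same visit, exact test: 39–43% for >50% at Month 1 (for example (66 − 40)/66 = 39%), 55–60% for >70% at Month 1, and 67–76% for >70% at Month 2. Uncorrected, the best count loses 24–28%. Against the four-month mean, the best exact count loses 43–45%.

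**5. A model that does not use the closure times.** Area remaining is lognormal (log SD 1), correlation is 0.2 to 0.6, and median control area remaining is 35% to 70%. Where a signed-rank test on area has about 80% power, exact McNemar has 18–47% at the 50% line and 24–49% at the 70% line. Against 80% these are losses of 41–78% and 39–70%. A mid-p McNemar reaches 32–58%, a loss of 27–60%. Only 3–11% of control wounds are more than 90% healed in this model, so it resembles Month 1 at most. It should not be joined to the ceiling in step 2 as one argument.

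**The case against.** Four points on the other side have weight.

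**The ceiling depends on the reading.** If 6 and 8.5 weeks are time spent closed, as the synopsis suggests, they are 6/16 = 37.5% and 8.5/16 = 53% of follow-up, and no ceiling follows. The synopsis also admits chronic open wounds and wounds that heal and re-blister, which would lower the Month 3 and Month 4 shares. This stands.

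**The loss depends on the test and the model.** The plan names no test. Exact McNemar is conservative (null rate 1–2% in the step 5 model), so part of the loss comes from the test and not from the threshold. With lognormal closure times on a linear path, the best count (>70% at Month 1) loses 27–29% even with the exact test. My check of that setting at correlation 0 gave 73% uncorrected against 86% for area, a loss of (86 − 73)/86 = 15%, and the four-month mean (71%) was no better than that one count. A reader might infer that the counts cost half the power or more as a matter of course. The documents give no figure from which that follows, and some settings contradict it. But the best count is known only in hindsight, and most of the eight do far worse.

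**Area has limits too.** On the linear path it has about 20% and 0% power at Months 3 and 4, so those visits are not lost through dichotomising. With an exponential path, lognormal times, correlation 0.5 and a reading error of 10 points, the four-month mean has 68% power, less than Month 1 alone (74%) but well above the best exact count (35%). Sizes at remote visits rest on home photographs with a ruler, and section 2.3.1 warns that an intact matrix can prevent assessment. Only the end of the phase is protected by a period without application, so readings at Months 1 and 2 may be missing in the matrix arm alone. The counts share this weakness.

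**Pairs are not independent.** At least 20 pairs come from 6–10 patients. The simulations ignore this, so their powers are benchmarks and not predictions.

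Finally, these are secondary endpoints of a pilot for which no power is claimed, and the primary endpoint is already continuous. That limits the weight of the point but does not remove the gain.

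**Conclusion.** The concern holds in a limited form. It needs no assumption to say that area is scheduled at baseline and monthly and that the secondary endpoints use it only as eight nested counts.

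The size does rest on assumptions. A count that is not at ceiling loses roughly a quarter to three quarters of the power of a paired analysis of percent area at the same visit. The low end comes from less conservative tests or skewed closure times, with about 15% in the most favourable setting checked. The high end comes from the exact test at Month 2. The ceiling at Months 3 and 4 holds only on the section 2.6.2 figures read as weeks to more than 90% closure with no re-opening.

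Two stronger inferences are not supported: that a continuous measure would rescue Months 3 and 4, and that the plan contains a wrong figure on this point.

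**What to change.** Make the lead secondary healing endpoint the within-pair difference in percentage of Day 0 area remaining, with a closed wound scored 0. Analyse it as one contrast averaged over Months 1 to 4, in a repeated-measures model with pair and patient effects. Treat a size that cannot be read because the matrix is intact as missing, and report the number of such readings by arm and visit. Keep the >50% and >70% counts as descriptive displays. Section 2.6.2 and the synopsis should also be reconciled on what the closure duration measures, because the expected ceiling depends on it.

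The cost is a change of endpoint and analysis wording and slightly more analysis work. No visit, measurement or subject is added. The downsides are reliance on area read from caregiver photographs and possible missing readings in the matrix arm at Months 1 and 2, where most of the gain lies.

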2.6.2 Sample size determination

We calculated that a sample size of 40 wounds (20 matrix-treated vs 20 untreated) would give us 90% power to detect a difference of 8.5 vs 6 weeks (SD=3) of wound closure duration between untreated vs matrix treated wounds respectively a two-sided alpha of 0.05. This sample size calculation is based on our prior natural history study of 720 RDEB wounds for 6 months in 13 RDEB adult and pediatric participants. We anticipate that the majority of pediatric wounds will be the recurrent type. If the Spincare matrix reduces the duration of wound closure, then this clinical trial would show a novel wound healing device that may improve wound closure duration in difficult to heal RDEB wounds. We would assess the secondary endpoints to determine if a 2.5-week shorter wound closure is clinically meaningful and associated with wound specific decreases in pain and itch.

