PRIMARY OBJECTIVE	
To assess the preliminary efficacy of matrix treatment in RDEB wound
 
To assess safety profile of matrix treatment in RDEB wound

SECONDARY OBJECTIVES	To assess improvement in wound pain with matrix treatment in RDEB wound To assess improvement in wound itch with matrix treatment in RDEB wound To assess caregiver responses on wound dressing ease of use with matrix treated wounds To compare the change in wound cultures between matrix treated wounds vs control wounds
NUMBER OF SUBJECTS	6-10 subjects for enrollment of at least 20 wound pairs
SUBJECT SELECTION CRITERIA	
Inclusion Criteria: Clinical and/or genetic diagnosis of RDEB by a dermatologist, age 6 years or older willing and able to give consent/assent and have at least 6 wounds (3 wound pairs) each with an area of 10cm² or greater located at any site (excluding face and genital skin). The first patient that will be enrolled is an adult patient before the recruitment of pediatric patients. Wounds must be present for at least 4 weeks and able to be classified as recurrent wounds (wounds that heal within 12 weeks but then re-blister) vs chronic open (older than 12 weeks).
 
Exclusion Criteria: Actively infected wounds with pus (colonized wounds are eligible), areas that have had squamous cell carcinoma (SCC), areas on the face and genitals, and areas that have been treated with investigational therapies in the past 3 months.

INVESTIGATIONAL DEVICE / INTENDED USE	Spincare The Spincare matrix is delivered from a portable, hand-held device that produces an electrospun healing matrix made of biocompatible materials that attaches directly to the wound bed.
CONTROL GROUP OR OTHER STUDY ARMS (if applicable)	Standard of care non-adhesive wound dressings and bandage changes currently used.
DURATION OF SUBJECT PARTICIPATION AND DURATION OF STUDY	Subjects will be on study for up to 4 months Screening: performed over phone and then virtually (up to 30 days before Day 0 treatment day) Treatment: 1-3 days (subjects to attend clinic) Follow-up: 4 months Open-Label Phase: 4 months The total duration of the study is expected to be 1 year. 4 months for subject recruitment and 6 months for final subject follow-up is anticipated.

CONCOMMITANT MEDICATIONS	Allowed: current EB medications (i.e., pain meds, vitamins, iron infusions, antibiotic ointments, oral antibiotics if needed). Prohibited: none

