2.5.3 Allocation to treatment

Intra-patient randomization and allocation of treatment is planned. Wounds will be matched according to wound characteristics e.g. size, severity, and location. Randomization will be computer generated.

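### The 90% power does not follow from its printed inputs (unpaired test: 73%), and true power cannot be determined without a named test, a within-pair correlation and an allowance for patient

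*Combined protocol and SAP*

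**What the plan says.** Section 2.6.2 and the Statistics row of the Protocol Synopsis give the same calculation: "a sample size of 40 wounds (20 matrix-treated vs 20 untreated) would give us 90% power", for means of 8.5 and 6 weeks, SD 3, two-sided alpha 0.05. Both cite a natural history study of 720 wounds in 13 participants as the source.

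The two places disagree on which group has which mean:

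- The Synopsis has "8.5 vs 6 weeks (SD=3) of wound closure duration between matrix treated vs untreated wounds". Its rationale row says "If the Spincare matrix decreases the duration of wound closure" and later wants to "determine if a 2.5 week longer wound closure is clinically meaningful".
- Section 2.6.2 has "8.5 vs 6 weeks (SD=3) of wound closure duration between untreated vs matrix treated wounds respectively" and wants to "determine if a 2.5-week shorter wound closure is clinically meaningful".

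On design, Section 2.5.3 says "Intra-patient randomization and allocation of treatment is planned", with wounds matched on characteristics such as size, severity and location. The Synopsis plans "6-10 subjects for enrollment of at least 20 wound pairs". Section 2.5.6 keeps recruitment open until 20 treated and 20 control wounds are reached.

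On analysis, the Synopsis row headed Primary Analysis Plan holds only sample size and recruitment text. Section 2.5.7 gives the intention-to-treat principle and an adherence sub-analysis. Section 2.6.3 gives expected results. None of them names a test or model for the primary endpoint.

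**The concern.** Two means, one SD and two groups of 20 read most naturally as an unpaired comparison, and that does not give 90%. The design points to a paired analysis, but the inputs for one are not printed: the SD of the within-pair difference, or a per-wound SD with a within-pair correlation. Nor is there any allowance for 20 or more pairs coming from only 6-10 patients, whose pair differences may resemble one another.

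This calculation is the only justification for the recruitment target. The study is meant to inform larger trials, and a null result cannot be judged against a power figure with no stated test behind it. The trial is also unblinded (Section 2.5.4), so leaving the test open allows it to be chosen after the data are seen.

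The reversed direction does not alter power, which depends on the size of the difference. It does leave open whether the endpoint is time until closure or time spent closed. That decides what SD 3 describes and how a wound still open at Month 4 is counted.

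**Working it through.** **Inputs from the plan:** 20 wounds per group, difference 8.5 − 6 = 2.5 weeks, SD 3, two-sided alpha 0.05, at least 20 pairs, 6-10 patients, and at least 3 pairs per patient (Section 2.4.3). **Assumed here, because the plan gives no values:** the within-pair correlation r and the intraclass correlation (ICC) of pair differences within patient. Power is from the noncentral t distribution unless marked as simulation.

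**1. Attempt to reproduce 90%, unpaired.** Noncentrality = 2.5 / (3·√(2/20)) = 2.635 with 38 df, giving **72.8%** (normal approximation 75.0%). With 31 per arm power is 89.8% and with 32 it is 90.7%, so 90% needs 32 per arm. Other readings of the same inputs also miss: one-sided t 82.7%; 40 per arm 95.7%.

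**2. Paired, SD 3 taken as the SD of the difference.** Noncentrality = 2.5·√20 / 3 = 3.727 with 19 df, giving **94.2%**. With 18 pairs it is 91.5%.

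**3. Paired, SD 3 taken as the per-wound SD.** SD of difference = 3·√(2(1 − r)), 20 independent pairs:

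| Assumed r | SD of difference | Power |
|---|---|---|
| 0 | 4.24 | 71% |
| 0.2 | 3.79 | 80% |
| 0.3 | 3.55 | 85% |
| 0.4 | 3.29 | 90% |
| 0.5 | 3.00 | 94% |

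Power is exactly 90% at r = 0.406 (SD of difference 3.27).

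**4. Allowing for patient.** Take a t-test on patient-mean differences, K patients with m pairs each, K − 1 df. The variance of a patient mean is SDdiff²·(1 + (m − 1)·ICC)/m. Example with K = 7, m = 3, SDdiff 3, ICC 0.2: variance = 9 × 1.4/3 = 4.2; standard error = √(4.2/7) = 0.775; noncentrality = 2.5/0.775 = 3.23 on 6 df; power 77%.

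| Patients and pairs | SDdiff 3, ICC 0 / 0.2 | SDdiff 4.24, ICC 0 / 0.2 |
|---|---|---|
| 6 patients, 20 pairs (4,4,3,3,3,3; simulated) | 84% / 69% | 56% / 42% |
| 7 patients × 3 pairs | 89% / 77% | 62% / 48% |
| 10 patients × 3 pairs | 98% / 93% | 82% / 68% |

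With per-wound SD 3, this test reaches 90% at r = 0.52 / 0.66 (ICC 0 / 0.2) for 7 × 3 pairs, and at r = 0.22 / 0.44 for 10 × 3 pairs.

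**5. Ignoring patient.** Suppose the matrix effect averages zero but varies between patients, with ICC 0.2. A paired t-test that treats all pairs as independent then has a simulated type I error of about 10% with 6, 7 or 10 patients, against the nominal 5%.

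**The case against.** The strongest reply is that the unpaired test is the wrong yardstick. Wounds are matched and randomized within patient, so a paired calculation was probably intended, and on one reading of SD 3 the 20 pairs give 94%. Only 18 are then needed for 90%, which leaves a small margin. Twenty pairs is also a floor: ten patients with three pairs each would bring 30, and a simple paired t-test on 30 independent pairs with per-wound SD 3 has 87.7% power at r = 0 and 93.7% at r = 0.2. The ICC of 0.2 and the patient-mean test are not in the plan. Finally, this is a single-site pilot of preliminary efficacy, where formal power matters less.

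Much of this stands. The finding does not show that the trial is underpowered, and 73% should not be read as its true power. But 94% is not the printed 90% either, and each route to 90% with 20 pairs needs something the plan does not state, such as a correlation near 0.41 or 18 pairs inflated for 10% dropout. Nothing printed shows that a natural history study supplied an SD of treated-minus-control differences. Thirty pairs is the best case, since recruitment may stop at 20. As for pilot status, the protocol chose to make a formal power claim and ties recruitment to it.

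**Conclusion.** The concern holds. The printed inputs give 72.8% unpaired or 94.2% if SD 3 is the SD of the paired difference, and 90% appears only with an added assumption. On the unpaired reading, a true 2.5-week difference would be missed about 27% of the time rather than 10%. Over the patient-level scenarios above, power runs from 42% to 98%. Those values rest on assumed correlations of 0 to 0.5 and ICCs of 0 to 0.2, none of them from the plan. The missing primary test and the contradictory direction of effect are matters of text and rest on no assumption. Because the figure sets the recruitment target and no primary analysis stands behind it, it must be corrected.

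**What to change.** 1. Reconcile the Synopsis with Section 2.6.2 on which group has 8.5 weeks and which has 6. State whether the endpoint is time to closure or time spent closed, and how wounds not closed by Month 4 are counted.
2. Name one primary analysis based on the within-pair difference that allows for patient. Examples are a t-test on patient-mean differences, or a mixed model with pair and patient-by-treatment effects and small-sample degrees of freedom.
3. Replace 90% with a power range for that same analysis at the low and high ends of 6-10 patients. State what SD 3 refers to and the assumed within-pair correlation and ICC. The cited natural history study may supply these values.

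If the sponsor nevertheless keeps the unpaired calculation, the figure to print is 73%, with a note that it reflects neither the pairing nor the patient clustering.

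The cost is a less favourable stated power, fewer degrees of freedom with a patient-level test, and a few sentences of text. Correcting the figure needs no extra patients or visits.
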